#### **6.6 Unscheduled Follow-up visits**

In the event that a patient visit for an issue associated with the device occurs outside the protocol-specified time frames (i.e., pre-discharge, 30 days, 6 and 12 months and annually from 2-5 years), then data will be recorded from that visit. Possible reasons for unscheduled visit related to the B-TEVAR procedure:

- Patient experiences new symptomology and/or an adverse event
- Surveillance of an existing adverse event

The unscheduled visit information would be recorded in the **Follow-up CRF** where the reason for the unscheduled visit will be specified. Only data pertinent to the reason for the unscheduled visit would be recorded.

#### **6.7 Discontinuation from study**

Patients who choose to discontinue participation in the study prior to study completion will be requested to undergo a final assessment by the investigator at the time notification is made of their decision to discontinue. The final assessment will be recorded in the **Follow-up and Study Completion - Exit CRFs**.

### **7.0 STUDY OBJECTIVES**

The purpose of this clinical trial is to evaluate the safety and effectiveness of physician modified endovascular grafts in the treatment of patients with thoraco-abdominal aortic aneurysms (TAAA).

#### **7.1 Primary Objectives**

The primary objective of this study is to determine if branched endovascular grafts are a safe and effective method of treating TAAAs. Treatment success is defined as successful deployment of the modified endograft and its branches with preservation of unimpeded flow to all target vessels that are intended to be preserved. Failure to exclude the aneurysm (i.e. Type 1 or 3 endoleak), conversion to an open operation, aneurysm rupture, thrombo-embolic complication to a target

vessel, kink/stenosis of a branch stent or flow limiting distal branch vessel dissection will be considered treatment failure. Any such branch related events that are identified intra-operatively and successfully treated will not be considered treatment failures.

The safety of the endovascular grafts will be determined by the proportion of patients with major adverse events. The effectiveness of the endovascular grafts will be determined by the proportion of patients that achieve treatment success.

## **8.0 DEFINITIONS**

### **8.1 Endoleak**

Endoleak is defined by the persistence of blood flow outside the lumen of the endovascular graft and within the aneurysm sac and can be classified as:

*Type I* – Ineffective seal at either the proximal or distal sealing zones

*Type II* – Retrograde blood flow from lumbar arteries, the inferior mesenteric artery, or other collateral vessels into the aneurysm sac

*Type III* – A leak caused by fabric tears or disruption, incomplete seal between components, component disconnection, or graft disintegration

*Type IV* – Blood flow through an intact fabric.

### **8.2 Migration**

Aortic stent graft migration is defined as evidence of proximal or distal movement of the stent graft > 10 mm relative to fixed anatomic landmarks. Spiral CT images will be used to determine migration at regularly scheduled follow-up visits. The 1 month image will be used as the baseline for subsequent assessment.

Branch stent graft migration is defined as evidence of movement of the branch stent graft in relation to fixed anatomic landmarks sufficient to induce a Type 1 or 3 endoleak after a branch had been documented to have adequate seal by CT imaging.

### **8.3 Patency/ Branch Vessel Patency**

Patency is defined as the preservation of unimpeded flow to the treated vessel. Thrombo-embolic complication to a target vessel, kink/stenosis of a branch stent or flow limiting distal branch vessel dissection will be considered loss of branch patency. This may be evidenced by: CT, angiography, ultrasound or other imaging modality, or pathological analysis. Flow limiting findings on screening CT scans or by elevated Creatinine will be evaluated with further confirmatory studies, including clinical examination, duplex, and angiography as indicated.

### **8.4 Loss of Stent Graft Integrity**

The integrity of the stent graft will be evaluated by abdominal CT scans at regularly scheduled follow-up visits. Any fractured stents, and any other issues compromising the integrity of the stent graft will be reported.

### 8.5 TAAA Enlargement

Aneurysm enlargement is defined as a greater than 5 mm (diameter) increase in the orthogonal plane of the aneurysm size. Spiral CT images will be used to determine aneurysm enlargement at regularly scheduled follow-up visits. The 1 month image will be used as the baseline for subsequent assessment.

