Study Secondary Endpoints	
The following secondary safety endpoints will be evaluated at 30 days, 12 months and annually to 5 years after implantation of the B-TEVAR device:
 
 
• Mortality rates
 
• Aneurysm related mortality
 
• Major Adverse Events (MAE)
 
• Conversion to open repair
 
• Aneurysm rupture
 
 
The following secondary effectiveness endpoints will be evaluated at 30 days, 12 months and annually to 5 years after implantation of the B-TEVAR device:
 
 
• Technical Success
 
• Freedom from Type I & III endoleaks
 
• Freedom from stent graft migration
 
• Freedom from aortic aneurysm enlargement
 
• Freedom from aneurysm rupture
 

	
 
• Freedom from conversion to open repair
 
• Radiographic evidence of device integrity
 
• Freedom from thromboembolic events
 
• Freedom from re-intervention
 

Clinical Utility Measurements	
The following Clinical Utility Measurements will be evaluated:
 
 
• Conduit usage
 
• Blood loss
 
• ICU stay
 
• Length of hospital stay
 
• Type of anesthesia
 
• Secondary interventions
 

Patient Population	
The total Treatment Group includes 60 patients, including those who are planning to undergo single or two-staged approach to repair.

Follow-Up Intervals	
Treatment Group follow up intervals will consist of 1, 6, and 12 months following the B-TEVAR implant procedure, then annually through 5 years.

Follow- Up Events	
Treatment Group follow up:
 
 
• Physical exam
 
• Contrast Enhanced Spiral Chest/Abdominal/Pelvic CT
 
• Device/aneurysm assessment based on imaging
 
• Laboratory Assessment
 
• Assessment of Adverse Events
 
• Assessment of concomitant medications (only anticoagulants, anti-platelets, antibiotics, statins, Beta blockers and ACE inhibitors/ARB)
 

Investigational Sites	
The University of Washington (University of Washington Medical Center and Harborview Medical Center) will be the only site involved in this trial.

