#### 9.1.2 Effectiveness

The primary effectiveness endpoint is the proportion of treatment group subjects that achieve treatment success with the B- TEVAR procedure, whether via the staged approach or done as a single procedure . Treatment success is a composite endpoint assessed at 12 months after the B-TEVAR procedure is performed that requires all of the following criteria to be met in order for a patient to be considered a treatment success:

- Technical Success, defined as successful delivery and deployment of the endovascular graft with preservation of unimpeded flow to those branch vessels intended to be preserved.
- Freedom from Type I & III endoleak. Type I and III endoleaks will be assessed by the investigator using Spiral CT images.
- Freedom from stent graft migration. Migration of the aortic stent graft is defined as evidence of proximal or distal movement of the stent graft >10 mm relative to fixed anatomic landmarks. Migration of a branch is defined as movement of the stent in relation to fixed anatomic location that results in a Type I or III endoleak. Spiral CT images will be used by the investigator to determine migration from the one month (baseline) CT image.
- Freedom from TAAA enlargement. Sac enlargement is an increase in aneurysm diameter (>5 mm) from the one month (baseline) post-operative measurement will be considered TAAA enlargement, as determined by the investigator.
- Freedom from TAAA rupture
- Freedom from conversion to open repair

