### 1.2.2 Secondary Effectiveness

The following secondary effectiveness endpoints will be evaluated at 30 days, 12 months and annually to 5 years:

- Need for re-intervention

- Treatment success as defined in section 9.1.2

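### Aortic migration and sac enlargement are listed for evaluation at 30 days, but the 30-day CT is their baseline, so neither can fail at that visit

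*Protocol*

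**What the plan says.** **Baseline.** Section 8.2 defines aortic migration as "evidence of proximal or distal movement of the stent graft > 10 mm relative to fixed anatomic landmarks". Section 8.5 defines enlargement as a "greater than 5 mm (diameter) increase in the orthogonal plane of the aneurysm size". Both sections then carry the same sentence: "The 1 month image will be used as the baseline for subsequent assessment". Section 9.1.2 builds this into the treatment-success composite: the investigator is to "determine migration from the one month (baseline) CT image", and enlargement is an "increase in aneurysm diameter (>5 mm) from the one month (baseline) post-operative measurement".

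**Time points.** In the Protocol Summary, "secondary effectiveness endpoints will be evaluated at 30 days, 12 months and annually to 5 years". The list that follows includes freedom from migration and freedom from enlargement as separate items. The body section on secondary effectiveness (headed 1.2.2; the table of contents has it as 9.2.2) uses the same time points for a shorter list: need for re-intervention and "Treatment success as defined in section 9.1.2". Section 9.1.2 itself sets that composite at 12 months.

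**Visit and imaging.** Section 6.5 equates the 1-month visit with day 30, with a window of 14 days either side. Section 8.7 and Appendix IV schedule a pre-procedure CT and then the 1-month CT, with no post-operative CT in between. Section 6.5 and Appendix IV also call for an imaging assessment that includes migration at the 1-month visit.

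**The concern.** An endpoint defined as change from a reference image cannot be evaluated on that image. The protocol fixes the 1-month CT as the reference and also asks for a result at 1 month. Taken at face value, every imaged subject is free of aortic migration and enlargement at 30 days, however the graft or sac behaved after implant.

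Three things are at stake:

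- Two 30-day figures in the Summary's endpoint list would look like evidence of early device stability but would contain none.
- The 30-day treatment-success rate would be decided by four components, while the 12-month rate is decided by six. With the same name on both, part of any fall between 30 days and 12 months would come from the definition.
- Because section 9.1.2 sets the composite at 12 months, the protocol does not say what a 30-day version of it means.

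**Working it through.** The protocol gives no target, rate or sample-size calculation for these endpoints, so there is no figure to reproduce. The check is first logical, then illustrative.

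**Step 1. Change at the 30-day visit.** Change = measurement on the current CT minus measurement on the baseline CT. At 30 days both are the 1-month CT, so change = 0 mm. Enlargement needs more than 5 mm and aortic migration more than 10 mm. Since 0 exceeds neither, no imaged subject can fail and each freedom is 100%.

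**Step 2. The six components of treatment success at 30 days.**

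| Component (9.1.2) | Can it fail at 30 days? |
|---|---|
| Technical success | Yes |
| Type I or III endoleak | Yes |
| Migration | No |
| Enlargement | No |
| Rupture | Yes |
| Conversion | Yes |

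Four of six carry information.

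**Step 3. Branch migration.** Section 8.2 counts it only "after a branch had been documented to have adequate seal by CT imaging", and it must produce a Type I or III endoleak. On scheduled imaging no earlier post-operative CT exists to document the seal, so it too is undetectable at 30 days. This adds no bias to the composite, because the endoleak already fails its own component. Any bias comes from aortic migration and enlargement only.

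**Step 4. Direction and possible size of the bias in the 30-day composite.** Let S be the success rate on the four components that can fail, and q the rate of isolated aortic migration or enlargement between implant and the 1-month CT. If the two are independent, the reported rate is S, the rate with early events counted is S(1 − q), and the difference is S × q. This cannot be negative. Neither S nor q is in the protocol; both are assumptions here (S from 80% to 95%, q from 0 to 10%).

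| q | S = 80% | S = 90% | S = 95% |
|---|---|---|---|
| 0 | 0 points | 0 | 0 |
| 1% | 0.8 | 0.9 | 0.95 |
| 2% | 1.6 | 1.8 | 1.9 |
| 5% | 4.0 | 4.5 | 4.75 |
| 10% | 8.0 | 9.0 | 9.5 |

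For example, with S = 90% and q = 5%, the report would show 90.0% against 0.90 × 0.95 = 85.5%. The range is 0 to 9.5 points and follows entirely from the assumed inputs.

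**Step 5. Apparent precision.** Even with all 60 enrolled subjects imaged, which is a ceiling, 60/60 gives an exact (Clopper-Pearson) 95% lower limit of 0.025^(1/60) = 94.0%. An interval of 94.0% to 100% would look informative although the result could not have been otherwise.

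**The case against.** **The wording already excludes 30 days.** Sections 8.2 and 8.5 make the 1-month image the baseline for later assessment, so the 30-day entry could be read as not applicable, and nothing tells the analyst to score the baseline scan as a success. That reading is sensible, but it does not remove the conflict: the Summary and the body still list a 30-day result that the definitions cannot produce. An analysis plan may settle the tabulation. The baseline and the time points, however, are both fixed in the protocol and disagree there.

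**The separate freedoms are not in the body's list.** This stands. They are 30-day endpoints only in the Summary; the body reaches them through treatment success.

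**A result of 60/60.** A reader might infer that the report would show 60 of 60. The documents do not support that. Subjects who die before the 1-month CT have no image, and the background in section 2.1.4 cites peri-operative or 30-day mortality of about 4% to 9% in branched-repair series. Converted subjects are followed by examination and adverse events only (8.6). Staged subjects who never receive the branched graft are analysed separately, without migration data (6.5). The denominator is unknown and likely below 60.

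**Early movement or growth is never counted.** A reader might infer this too, and it goes too far. An early event that causes a Type I or III endoleak, rupture or conversion fails the corresponding component, and re-intervention is a separate endpoint. What escapes is silent displacement or growth before the 1-month scan, which the window allows as late as day 30 + 14 = 44.

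**The consequence is small.** This is a single-arm feasibility study, and no stated decision rests on the 30-day figures. That stands and limits the weight of the point.

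**Conclusion.** The inconsistency is real and limited to the 30-day evaluation. Among subjects with a 1-month CT, freedom from aortic migration and freedom from enlargement are 100% by definition at that visit, and the 30-day composite rests on four of its six components while sharing the 12-month composite's name.

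Any bias in the 30-day composite is upward. Its size cannot be derived from the protocol: it is zero if no isolated aortic migration or enlargement occurs before the 1-month CT, and 0 to 9.5 points under the assumed ranges above. Actual inflation is therefore possible but not shown.

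A reader might also infer that the primary effectiveness endpoint is compromised. It is not made degenerate: at 12 months the current scan and the 1-month baseline are different images, and a post-operative baseline is a workable choice from 6 months on. The conclusion assumes that no earlier post-operative image is used as the reference, as the schedule implies. It applies only to subjects who have the 1-month CT.

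**What to change.** 1. In the Protocol Summary and the secondary effectiveness section, report aortic migration and enlargement only from the first scheduled evaluation after the 1-month baseline. Under the present time points that is 12 months; a 6-month CT is scheduled if an earlier report is wanted. Mark both items as not applicable at 30 days.
2. Define 30-day success separately as technical success plus freedom from Type I or III endoleak, rupture and conversion. Give it a different name from the 12-month composite, so that the two are not read as one series.
3. Optionally, add a descriptive sensitivity analysis of sac diameter change from the pre-procedure CT. That scan may be up to 4 months old (6.2, Appendix IV) and can include growth before implant: at the 0.5 cm in 6 months that qualifies a patient under section 5.1.1, 5 mm × 4/6 = 3.3 mm could accrue beforehand. It cannot serve as a migration baseline, because no graft is yet in place.

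Items 1 and 2 are changes of wording only; the cost is the loss of two uninformative 30-day figures. Item 3 uses scans already required. No new visit, scan or subject is needed.

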### 8.6 Surgical Conversion

Surgical conversion occurs when a patient implanted with a physician modified endovascular graft undergoes open surgical repair with explantation of the stent graft. The follow-up for patients who are converted to open surgical repair include collection of the following data: Physical Exam and assessment of Adverse Events. The visits are to occur at 1 month post open conversion and 1 year post open conversion.

### 8.7 Imaging

Study Visit	Images Retained by Investigator
Baseline	Contrast Enhanced Spiral CT of the Chest/Abdomen/Pelvis
1 month	Contrast Enhanced Spiral CT of the Chest/Abdomen/Pelvis or Non-contrast fine cut CT of the Chest/Abdomen/Pelvis with visceral artery duplex if the patient cannot receive IV contrast
6 month	Contrast Enhanced Spiral CT of the Chest/Abdomen/Pelvis or Non-contrast fine cut CT of the Chest/Abdomen/Pelvis with visceral artery duplex if the patient cannot receive IV contrast
12 month and annually for 5 years	Contrast Enhanced Spiral CT of the Chest/Abdomen/Pelvis or Non-contrast fine cut CT of the Chest/Abdomen/Pelvis with visceral artery duplex if the patient cannot receive IV contrast

\*Refer to **Appendix VI: CT Scanning Techniques** imaging requirements.

**Patients who have the first stage repair will be imaged with a spiral CT of the Chest/Abdomen/Pelvis with or without contrast at 1 and 12 months and annually to 5 years or until they undergo the second B-TEVAR stage. Following the second stage, they will undergo imaging as described above at 1, 6, 12 months and annually for 5 years from the date of the second stage.**

### 8.8 Explant Evaluation

The investigator is committed to understanding the effects of the human *in vivo* environment on the stent graft over time. To this end, all explanted devices will be evaluated by a Pathologist at the University of Washington. Refer to **Appendix VII: Explant Procedure** for specific instructions for managing the removal and handling of the explanted TAAA device.

### 8.9 Adverse Events

An adverse event is any new, undesirable medical occurrence or change (worsening) of a pre-existing condition that occurs in a patient, whether or not considered to be associated with the

product. Elective hospitalizations for pre-existing conditions are not adverse events. Requirements for reporting AEs are dependent upon the reviewing IRB policy. Adverse events will be reviewed by a Clinical Events Committee (CEC). The CEC will meet periodically, a minimum of annually. Adverse Event information is recorded in the **Adverse Event CRF**.

For purposes of this study, the following events are not considered adverse events, because they are expected to occur in conjunction with the index procedure or are associated with customary, standard care of patients undergoing endovascular TAAA repair procedures:

- Early post-operative pain (within 72 hours of index procedure) at the access site and/or related to position on procedure table (i.e. low back pain, abdominal pain, groin pain)
- Post-anesthesia/conscious sedation emesis, nausea, or headache (within 72 hours of index procedure)
- Electrolyte imbalance without clinical sequelae following index procedure, even if requiring correction
- Low grade temperature increase (< 100.5 °F)
- Blood loss not requiring transfusion
- Minor, localized tenderness, swelling, induration, bruising, erythema, hematoma etc. at vascular access site that does not require surgical intervention, evacuation, transfusion, or antibiotics
- Non-sustained arrhythmia not requiring treatment or intervention
- Prophylactic administration of atropine
- Prophylactic pacing
- Isolated, non-sustained PVCs/PACs
- Asymptomatic hypotension or hypertension
- Use of vaso-active medications for asymptomatic hypotension in the setting of routine spinal cord protection
- Atelectasis not requiring treatment
- Pleural effusion(s) not requiring treatment
- Urinary retention or hematuria not requiring intervention other than urinary drainage
- Thrombocytopenia not requiring transfusion
- Leukocytosis not requiring treatment
- Delirium, confusion or agitation within the first 72 hours postoperative unless such is found to be attributable to a TIA or Stroke or other new medical condition
- Constipation
- Chest pain that is determined to be non-cardiac in origin
- Peripheral edema not requiring treatment other than diuresis
- Shortness of breath not requiring treatment other than diuresis
- Bruising
- Loss of appetite/anorexia requiring medical treatment
- Weakness not due to spinal cord injury (i.e. fatigue and deconditioning)

The Investigator and/or IRB may require that these events are reported as adverse events. In this case, the Investigator will report these observations based on his medical judgment and requirements of the IRB.

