### **8.11 Major Adverse Events (MAE)**

The following specific events will be considered major adverse events (MAE) for the purpose of evaluating the primary (30 day) and secondary (1 year) safety endpoints:

- Death
- Paralysis (excludes paraparesis)
- Myocardial Infarction
- Stroke (excludes TIA)
- Renal Failure (excludes renal insufficiency)
- Respiratory Failure (excludes COPD or pulmonary complications)
- Bowel Ischemia
- Lower Extremity Ischemia
- Procedural Blood Loss ( $\geq 1,000$  cc)

A MAE may or may not be considered related to the device. Mortality will be reported as “all cause” and “TAAA related.” All deaths occurring in the first 30 days post-index procedure are considered “TAAA related.”

The Clinical Events Committee (CEC) shall determine which adverse events in addition to those listed above in Section 8.11 are considered Major Adverse Events for evaluation of the primary (30 days) and secondary (1 year) safety endpoints.

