### 12.2 Clinical Events Committee

The Clinical Events Committee (CEC) will be used to review and adjudicate all device related adverse events and all serious adverse events regardless of the relatedness to the device. The

CEC shall also determine which adverse events (other than those listed in Section 9.1.1) are considered Major Adverse Events for evaluation of the primary and secondary safety endpoints. The committee shall consist of at least three (3) physicians representing multiple specialties familiar with thoraco-abdominal aortic aneurysm repair. The CEC will be comprised of Drs., [name], [name], [name] and [name]. [name] is a Professor of Surgery and Director of Surgical Critical Care at Harborview Medical Center. [name], is an Acting Instructor in the Department of Medicine and a member of the Medicine Consult Service at University of Washington Medical Center and the Seattle Cancer Care Alliance. [name] is a Clinical Professor with the Department of Pain and Anesthesia.. [name] PhD is an Associate Professor of Anesthesiology with expertise in the study of quality and safety. The CEC will provide their review to the DSM and will meet annually at a minimum.

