**1.2 Adverse Event and Serious Adverse Event Collection and Reporting**

An adverse event (AE) is any new, undesirable medical occurrence or change (worsening) of a pre-existing condition that occurs in a patient, whether or not considered to be associated with the product. Elective hospitalizations for pre-existing conditions (e.g., elective cosmetic procedures) are not adverse events. Requirements for reporting AEs are dependent upon the reviewing IRB policy. Adverse events will be reviewed by a Clinical Events Committee (CEC). The CEC will meet periodically, a minimum of annually. Adverse Event information is recorded in the **Adverse Event Case Report Form (CRF)**.

For purposes of this study, the following events are not considered adverse events, because they are expected to occur in conjunction with the index procedure or are associated with customary, standard care of patients undergoing endovascular AAA repair procedures:

- Early post-operative pain (within 72 hours of index procedure) at the access site and/or related to position on procedure table (i.e. low back pain)
- Post-anesthesia/conscious sedation emesis, nausea, or headache (within -72 hours of index procedure)
- Electrolyte imbalance without clinical sequelae following index procedure, even if requiring correction
- Low grade temperature increase (< 100.5 °F)
- Blood loss not requiring transfusion and not resulting in decreased hematocrit.

- Minor, localized tenderness, swelling, induration, bruising, erythema, hematoma etc. at vascular access site that does not require surgical intervention, evacuation, transfusion, or antibiotics
- Non-sustained arrhythmia not requiring treatment or intervention
- Prophylactic administration of atropine
- Prophylactic pacing
- Isolated, non-sustained PVCs/PACs
- Asymptomatic hypotension or hypertension
- Use of pressor medications for asymptomatic hypotension in the setting of routine spinal cord protection
- Atelectasis not requiring treatment
- Urinary retention or hematuria not requiring intervention other than urinary drainage
- Thrombocytopenia not requiring transfusion
- Mild leukocytosis not requiring treatment

The Investigator and/or IRB may require that these events are reported as adverse events. In this case, the Investigator will report these observations based on his medical judgment and requirements of the IRB.

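### Section 8.9 excludes untransfused blood loss from adverse events without a volume limit, although a procedural loss of 1,000 cc or more is a component of the primary safety endpoint

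*Protocol*

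**What the plan says.** Section 8.9 opens its exclusion list with "For purposes of this study, the following events are not considered adverse events, because they are expected to occur in conjunction with the index procedure" and includes "Blood loss not requiring transfusion". The item has no volume ceiling and no exception for events that count as MAEs. The same section sends adverse events to the Adverse Event CRF and to CEC review. An override follows the list, but it is discretionary: "The Investigator and/or IRB may require that these events are reported as adverse events".

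Section 8.11 introduces the list that defines the safety endpoints with "The following specific events will be considered major adverse events (MAE) for the purpose of evaluating the primary (30 day) and secondary (1 year) safety". That list includes "Procedural Blood Loss" at a threshold of 1,000 cc or more, with no transfusion condition. Section 9.1.1 repeats the list for the primary safety endpoint.

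Appendix IX, section 1.2, restates the exclusion as "Blood loss not requiring transfusion and not resulting in decreased hematocrit".

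Three other places bear on capture. Section 6.3 records the estimated blood loss and any replacement on the Procedure – System Evaluation CRF. Section 9.2.1 has the CEC meet annually to review all MAEs. Section 12.2 describes the CEC's task as to "review and adjudicate all device related adverse events and all serious adverse events".

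**The concern.** The same event is defined in two incompatible ways. A subject who loses 1,000 cc or more without transfusion has a primary-endpoint event under 8.11 and 9.1.1, and by 8.9 has no adverse event at all. No section says which rule prevails.

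What is at stake is complete ascertainment of one component of the primary safety endpoint. If MAEs are assembled from Adverse Event CRF entries, site staff who follow 8.9 will not have entered these subjects, and the observed 30-day MAE proportion can only fall. If the component is derived from the recorded volume, they are all counted. The protocol does not say which source is used. It names blood loss elsewhere only as a clinical utility measure (Protocol Summary and section 9.3).

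**Working it through.** The protocol states no figure to reproduce here, so the check compares the rules case by case.

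**Rules**
- Section 8.9: not an adverse event if there is no transfusion.
- Appendix IX 1.2: not an adverse event if there is no transfusion and no fall in hematocrit.
- Sections 8.11 and 9.1.1: an MAE if the procedural loss is 1,000 cc or more.

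| Loss | Transfused | Hematocrit falls | 8.9 | Appendix IX 1.2 | 8.11 / 9.1.1 |
|---|---|---|---|---|---|
| under 1,000 cc | no | no | excluded | excluded | not an MAE |
| under 1,000 cc | no | yes | excluded | not excluded | not an MAE |
| 1,000 cc or more | no | no | excluded | excluded | **MAE** |
| 1,000 cc or more | no | yes | excluded | not excluded | **MAE** |
| 1,000 cc or more | yes | either | not excluded | not excluded | MAE |

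Rows 3 and 4 are the conflict between 8.9 and the endpoint. Rows 2 and 4 show that the two exclusion lists also disagree with each other.

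**Is the omission deliberate?** Neighbouring items in the 8.9 list are worded to protect serious outcomes. Early delirium is excluded only when it is not traced to a TIA, stroke or other new condition, chest pain only when it is non-cardiac, and weakness only when spinal cord injury is not the cause. Blood loss has no such limit, which suggests an oversight.

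**Route of the event.** Sections 8.10 and 8.12 name the Adverse Event CRF for serious adverse events and unanticipated device effects. Section 8.11 names no form for MAEs. Section 6.3 puts the volume on the Procedure CRF for every procedure, but no section links that field to the MAE component.

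**Scale.** Section 5.0 gives 60 subjects. If k subjects have a loss of 1,000 cc or more, no transfusion and no other MAE, and all are missed, the proportion falls by k/60:
- k = 1: 1/60 = 1.67 points
- k = 2: 2/60 = 3.33 points
- k = 3: 3/60 = 5.0 points

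The condition of no other MAE matters, because a subject with another component already counts. The 60 include subjects enrolled for a staged repair. Section 6.5 analyses those who never reach the second stage separately, so the B-TEVAR denominator may be below 60 and the shift per subject slightly larger.

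The protocol gives no frequency for such subjects. As an assumption, let q be their share. The chance that at least one occurs is 1 − (1 − q)^60, which gives 45% at q = 1%, 70% at q = 2% and 95% at q = 5%. This is the chance that such a subject exists, not that one is missed.

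**The case against.** The case on the other side is substantial, and most of it stands.

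- **The endpoint definition is self-contained.** Neither 8.11 nor 9.1.1 requires an event to qualify first under 8.9. As the more specific rule, the MAE list would sensibly prevail. That is the better reading, but the protocol does not state it.
- **The data exist.** The Procedure CRF holds the estimated volume for every procedure, so the component can be derived for everyone. This stands, and it is why the problem is one of possible rather than certain loss.
- **CEC review.** From 12.2 alone, a reader might infer that an excluded event never reaches the CEC. The documents do not support that, because 9.2.1 puts all MAEs before the committee. What remains is that 9.2.1 names no form by which an event classed as no adverse event would arrive.
- **Source of the endpoint.** A reader might also infer that the primary rate is computed from an adjudicated adverse-event file and is therefore biased downward. No section says so, and the choice of source field may properly be left to an analysis plan that is not shown. The definition of an adverse event and what sites enter on its form are, however, protocol content.
- **Size.** It is tempting to use the institution's juxta-renal series in section 2.1.4 (mean blood loss 200 cc, maximum 1,000 cc) as evidence of frequency. It concerns a different procedure and gives neither transfusion data nor the number of patients at the threshold, so it cannot support an estimate.

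**Conclusion.** The contradiction is in the text and is unresolved: 8.9 removes from adverse events a class of losses that 8.11 and 9.1.1 count in the primary safety endpoint, and Appendix IX 1.2 words the exclusion differently again. The supported conclusion is that such an event can be missed if MAEs are taken from Adverse Event CRF entries. It is not that the event will be missed or that the published rate will be biased.

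The effect is about 1.7 percentage points per missed subject, assuming a denominator of 60 and no other MAE in that subject. How many subjects this concerns is unknown. The point is correctable and of moderate weight; it deserves attention because it touches the primary safety endpoint and costs little to settle.

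**What to change.** 1. In section 8.9 and Appendix IX 1.2, state that the exclusion list does not apply to any event listed in 8.11 and 9.1.1.
2. In 8.11 or 9.1.1, state that the blood-loss MAE is derived from the volume on the Procedure CRF regardless of transfusion, and that it goes to the CEC with all other MAEs.
3. Reconcile the two versions of the blood-loss exclusion, with and without the hematocrit condition, as an explicit decision. Writing one volume-capped sentence into both places would silently drop the hematocrit condition from Appendix IX, and with it the reporting of smaller losses that lower the hematocrit.

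The cost is a few lines of text. No new data are needed, since the volume is already collected. The observed MAE rate may be slightly higher.
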